
1b. Patient Usability (patient perspective): We will also conduct a focus group with the initial 10 patients enrolled in the intervention arm of the study to obtain user feedback regarding any barriers to implementation or usability suggestions to further adapt the intervention if necessary before additional participants are enrolled. The qualitative methods detailed above will be employed. The patient focus group will take approximately two hours and will be conducted in a confidential conference room at NUMC. Patient participants will be compensated \$50 for their participation. The discussion guide for the patient focus group will be developed by the Drs. [name] and [name] with input from the CAB (see Appendix 2). Discussion topics include (but are not limited to) the following: 1) patients' perceptions of the ease of the study implementation (using the equipment, uploading) 2) patients' perceptions of usefulness of the intervention; 3)

patients' input on barriers/challenges to intervention implementation; and 4) suggestions for improvements and/or adjustments that should be made. Data will be coded and analyzed using NVivo (see above) to identify the barriers and challenges that need to be addressed as study implementation continues in order to ensure a high level of usability.

Patient Utilization: This phase of intervention development will also involve an ongoing process evaluation of usability using quantitative methodology. Again, this is so that adjustments can be made, as necessary, as the TSM intervention is implemented.

We will operationalize usability using the following measures:

- 1) Rate of acceptability
- 2) Rate of installation acceptance
- 3) Upload compliance
- 4) Total number of visits
- 5) Patient satisfaction

Aim 2: we propose to conduct the first randomized controlled trial to telemonitor minority community-dwelling patients with CHF (NYHA class1-3) for 3 months after hospital discharge or CHF. We will compare hospital and emergency room utilization, as well as QoL, between TSM and standard of care groups.

This is a prospective randomized controlled trial of 104 community-dwelling patients from disparity communities living with CHF 18 years and older.

In this study, patients will be randomized either to TSM or to standard of care once they have given consent to participate to *directly compare TSM to standard of care* in a health disparity population.

Table 1. Proposed Intervention: TSM and Standard of Care (SOC)		

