Upload compliance: We are arbitrarily defining three levels of compliance: High, moderate and minimal. "Minimal" compliance is defined as at least one upload per week for 6 out of the 12 weeks. "Moderate" compliance is defined as at least one upload per week for 9 out of the 12 weeks, and "High" compliance is defined as at least three uploads per week for 9 out of the 12 weeks. *A secondary compliance measure will be the number of uploads over* the 90 day period. = u/d. (maximum number of possible uploads = 90). All of these measures will be appropriately prorated for patients who die, or are hospitalized during the study, and are therefore not subject to uploading requirement during those times. With a sample size of 52 patients, the rates of compliance can be estimated to, at worst, +- 13.9%, with a 95% CI.

Total number of visits: We will compute the proportion of 12 scheduled visits that are kept. Therefore, if a patient is being followed for *w* weeks, there should be *w* scheduled visits. If the number scheduled visits that are kept is denoted by *v*, then the proportion of scheduled visits kept = v/w. Visit participation rates will be averaged across patients, and the mean rate will be computed, along with 95% confidence intervals. There is a maximum of 12 possible telehealth visits over the 3 month study period.

Patient satisfaction: We will measure patient perceptions of usability using a slightly modified version of the Telemedicine Satisfaction and Usefulness Questionnaire (Appendix 3). This 22-item questionnaire, which utilizes a 5 point Likert scale, will elicit a total sum score of satisfaction/usability that will then be dichotomized into satisfied vs. not satisfied based on previous literature.

Sample size considerations: We will randomize 116 patients as they are discharged from the hospital (58 per arm) in order to yield a maximum of 52 patients in the TSM arm of the study over a two year period.

These scores will be assessed using mean scores, percentages and histograms.²⁵ For satisfaction rates of 50%, 75% and 90%, with a sample size of 52, the corresponding 95% confidence intervals will have precision of +/- 13.9%, 12.7%, and 8.3%, .

Aim 2: we will measure inpatient utilization, emergency room utilization and QoL of patients receiving telehealth technology vs. standard of care patients.

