2a. Measures of Inpatient Utilization. Inpatient utilization will be measured in three ways, including: 2a.1) whether an individual subject had at least one inpatient hospitalization over the 3 month period; 2a.2) the number of hospitalizations experienced by an individual subject over the 3 month period; and 2a.3) cumulative length of stay (LOS) (inpatient days) experienced by an individual subject over the 3 month period (i.e., for multiple hospitalizations, the sum of all LOS's will be computed as the cumulative LOS). Cumulative LOS will be analyzed in two ways: intention to treat (ITT) analysis, and for only those hospitalized. The ITT analysis will include all patients, regardless of hospitalization history, to address the bigger public health issue: does TSM have an impact on LOS overall? A secondary analysis will look at LOS only for those who experienced a hospitalization. Finally, after ITT analysis, secondary analyses will include covariate adjustments for possible confounders.

Statistical Methods: Inpatient Utilization. For outcome 2a.1, the proportions of patients in each group who were hospitalized will be compared using the standard Chi-square or Fisher's exact test. Associated 95% confidence intervals for these proportions and their differences will be computed using exact methods. For outcome 2a.2, the number of hospitalizations will be compared using Poisson regression (SAS PROC GENMOD). It is likely that, due to excess zeros (i.e., zero inflation), methods for overdispersed Poisson will be required. Another approach for both outcomes 2a.2 and 2a.3 will be to use Lachenbruch's two stage procedure for zero-inflated data.30 For these primary ITT analyses, no adjustments will be made for any covariates.

Sample size considerations: We expect to enroll 52 patients in the TSM group which will yield the necessary statistical power.

2b. Measures of ER Utilization, defined as: 2b.1) whether or not an individual subject had at least one ER visit over the 3 month period; and 2b.2) the number of ER visits experienced by an individual subject over the 3 month period. Covariate adjustments will be made for potential confounders.

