Statistical Methods: ER *Utilization*: The statistical methods for analyzing ER utilization outcomes will be similar to those presented for inpatient utilization. Specifically, for outcome 2b.1, the proportions of patients in each group who utilized the ER will be compared using the standard Chi-square or Fisher's exact test. Associated 95% confidence intervals for these proportions and their differences will be computed using exact methods. For outcome 2b.2, (overdispersed) Poisson regression will be used. For outcome 2b.2, Lachenbruch's two stage procedure for zero-inflated data will also be considered.²⁵

Sample Size Considerations. The sample size and power considerations identified for outcomes 2a.1 and 2a.2 are virtually identical for ER utilization.

2c. Quality of Life assessment: We will use the Minnesota Living with Heart Failure Questionnaire²⁷ (Appendix 4) to assess patient QoL (QoL). While HF will continue to impact the lives of these patients, it is reasonable to believe that proper disease management via telehealth will improve QoL due to earlier exacerbation detection and lowered hospital utilization. We will compare questionnaire results between patients receiving TSM and usual care patients. Measures of QoL are defined as the 3 month QoL score minus the 1 month QOL score, where a positive score indicates a worsening of QoL .

Statistical Methods. A two-sample z-test will be used to compare changes in QoL between groups.

Sample size and power considerations. we expect to enroll 52 patients in each group, a 2-sample z test (80% power) to detect an effect size of 0.39 or greater, which is considered "small" to "medium".²⁸

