## A Randomized, Controlled Trial Comparing Telehealth Self-Management to Heart Failure Clinic Outpatient Management in Black and Hispanic Disparity Patients Living with Heart Failure

[name], [name], MA, [name], [name], [name], [name], NP, [name], MS, [name], [name], [name], LMSW, [name], MSN, [name], and [name], MPH

The health system's Biostatistics Unit created a randomization schedule for patient assignment, to randomize patients to either TSM or COM using permuted block randomization, with stratification by heart class, to ensure equal representation of heart class across the two groups. The primary analysis of this randomized clinical trial was based on intention to treat (ITT) principle, which included all subjects randomized. Descriptive statistics are presented as means, standard deviations, medians, ranges and frequency/percentages.

Inpatient utilization was defined in three ways, including: 1) whether an individual patient had at least one inpatient hospitalization over the 90 day period; 2) the number of hospitalizations experienced by an individual patient over the 90 day period; and 3) the cumulative length of stay (LOS) (inpatient days) experienced by an individual patient

over the 90 day period (i.e., for multiple hospitalizations, the sum of all LOS's was computed as the cumulative LOS).

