ED utilization was defined as whether or not an individual patient had at least one ED visit over the 90-day period. Binary outcomes for ED visits and hospitalizations were analyzed using the standard Chi-square or Fisher's exact test. Associated 95% confidence intervals for these proportions and their differences were computed using exact methods. The number of ED visits as well as hospitalizations within each group were separately compared using Poisson regression (SAS PROC GENMOD). Due to excess zeros (i.e., zero inflation), methods for over dispersed Poisson were required for both ED visits and hospitalizations. Cumulative LOS (inpatient days) was analyzed using a negative binomial regression. HF-related hospitalizations, ED visits, and LOS were analyzed in the same fashion described above, as were cardiovascular related outcomes. Reasons for ED visits as well as hospitalizations were classified as: HF alone (yes/no), cardiovascular related alone (yes/no), or both by the clinical team.

Repeated measures analysis of variance (RMANOVA) with a mixed models approach was used to compare changes at enrollment and at 90 days between groups. New York Heart Association (NYHA) class, PHQ-4, MLHFQ Physical and Emotional subscales were also analyzed using RMANOVA. The subscales of Anxiety and Depression, as measured by the PHQ-4, were dichotomized to presence or absence and Generalized Estimating Equations (GEE) were used to analyze these binary data. Days at home was

calculated as a proportion of days spent out of hospital during the 90 day period. The two groups were compared using the Mann-Whitney test.

Subgroup analyses included: patients hospitalized, heart class (2 vs. 3), and patients not receiving home care (prevalent in disparity populations). For the TSM group only, adherence was calculated, with low adherence defined as less than 10 vital signs uploads over the 90 day period.

Sample size and power calculations were based on previous literature and preliminary data from a non-disparity randomized RCT TSM study. We hypothesized that 75% of patients in the COM group would be hospitalized at least once during the study period and that TSM would reduce that rate to 50% (a relative reduction of 50%). The calculation was based on a chi-square test (alpha=0.05, two-tailed) with an n=52 patients per group. All analyses were performed using SAS 9.4 (SAS Institute Inc., Cary, NC).

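### The documents give incompatible sample sizes (116 or 104 randomized, 58 or 52 per arm), and the 52-per-group power basis does not match an intention-to-treat analysis of all 116 randomized

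*Protocol*

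**What the plan says.** The number of patients appears in five places.

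- Protocol, Criteria for Evaluating Response/Statistical Analysis, Aim 1, sample size paragraph: "We will randomize 116 patients as they are discharged from the hospital (58 per arm) in order to yield a maximum of 52 patients". The sentence goes on to place the 52 in the TSM arm, over two years.
- Protocol, Experimental Design, Aim 2: "This is a prospective randomized controlled trial of 104 community-dwelling patients".
- Protocol, section 2a (inpatient utilization), sample size paragraph: "We expect to enroll 52 patients in the TSM group which will yield the necessary statistical power". No power figure is given.
- Protocol, section 2c (quality of life): "we expect to enroll 52 patients in each group, a 2-sample z test (80% power) to detect an effect size of 0.39 or greater".
- SAP, sample size paragraph: "The calculation was based on a chi-square test (alpha=0.05, two-tailed) with an n=52 patients per group". The rates are 75% hospitalized at least once in the control group and 50% under TSM. No power figure is given.

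On who is analysed, the SAP says that the primary analysis follows the "intention to treat (ITT) principle, which included all subjects randomized". Protocol section 2a also calls its main comparisons ITT analyses.

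Two further passages bear on the count. Under Aim 1 the protocol recognises that some patients randomized to TSM may not accept the equipment at home. Under Recruitment Procedures it describes randomization to either arm, and then has the nurse tell patients that telehealth enrolment is over and that they will join standard of care.

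**The concern.** A trial has one number randomized, and under intention to treat that is also the number in the primary analysis. Here 116 and 104 both stand as the size of the trial, and 58 and 52 both stand as the size of an arm. The power basis is 52 per group, whereas an analysis of everyone randomized would have 58 per arm if 116 is right.

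Two things are at stake. First, the reader cannot tell what power the primary comparison has, because neither document states a power for the hospitalization test and the number to use is ambiguous. Second, the gap between 58 and 52 is unexplained. Declining installation or abandoning daily uploads can occur only in the TSM arm, so the plan should say outright that such patients stay in the between-group comparison. At present this follows only from the general ITT statement, while the group sizes quoted for Aim 2 point to a smaller set.

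**Working it through.** **Inputs.** Control rate 75%, TSM rate 50%, chi-square test, alpha 0.05 two-tailed, 52 per group (SAP sample size paragraph). 116 randomized, 58 per arm (protocol, Aim 1). 104 in total (protocol, Experimental Design, Aim 2).

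**1. Do the counts agree?** 2 × 52 = 104 and 2 × 58 = 116. The difference is 12 patients, 6 per arm, or 6/58 = 10.3% of each arm. The Aim 1 sentence gives 52 for TSM only. The 52 in each group comes from protocol section 2c and the SAP.

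**2. Can the SAP's 52 be reproduced?** The SAP gives no power for this test, so I assume 80%, the figure in the quality-of-life paragraph. With mean rate 0.625:

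n = [1.960 × √(2 × 0.625 × 0.375) + 0.842 × √(0.75 × 0.25 + 0.50 × 0.50)]² / 0.25² = 57.7, so 58 per group.

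This does not return 52.

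**3. Where could 58 come from?** Either from step 2, or from inflating 52 for a 10% loss: 52/0.90 = 57.8, so 58, and 104/0.90 = 115.6, so 116. Both routes give 58. The documents state neither a 10% loss nor 80% power for this test, so they do not settle the origin.

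**4. Power at 75% versus 50%.** Normal approximation: power = Φ{[0.25√n − 1.960 × √0.46875] / √0.4375}.

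- n = 52: (1.803 − 1.342)/0.661 = 0.697, power 75.7%.
- n = 58: (1.904 − 1.342)/0.661 = 0.850, power 80.2%.

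Exact enumeration of the uncorrected chi-square test gives 77.2% at 52 and 79.9% at 58. The exact figures are used from here on.

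**5. Sensitivity to non-uptake at 58 per arm.** Assume that 6 of the 58 TSM patients do not take up the intervention but stay in the analysis, and that the other 52 have the planned 50% rate.

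| Benefit in the 6 | TSM rate over all 58 | Exact power vs 75% |
|---|---|---|
| None (rate 75%) | (52 × 0.50 + 6 × 0.75)/58 = 52.6% | 71.3% |
| Half (rate 62.5%) | (52 × 0.50 + 6 × 0.625)/58 = 51.3% | 75.8% |
| Full (rate 50%) | 50% | 79.9% |

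**6. If 104 was intended.** With 52 per arm and 6 TSM patients not taking up the intervention, no benefit gives (46 × 0.50 + 6 × 0.75)/52 = 52.9% and power 66.9%. Half benefit gives (46 × 0.50 + 6 × 0.625)/52 = 51.4% and power 72.3%.

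**The case against.** Randomizing more patients than the powered number is ordinary practice and compatible with intention to treat. Both documents name ITT, so an analyst has no instruction to analyse completers. The sentence with 116 sits under Aim 1, beside the precision of the satisfaction rates, and gives 52 for the TSM arm alone. Using 52 for usability among TSM users conflicts with no Aim 2 rule. Without dilution, analysing all 116 raises power.

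This stands, and it limits the point. A reader might infer that the 52-per-group basis assumes dropouts leave the analysis, or that recruitment runs until 52 retained TSM patients are reached. The documents do not support either inference. They contain no attrition rate, no replacement rule and no exclusion rule, and sections 2a and 2c speak of enrolling 52, not of completing.

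The dilution figures are also conditional. The SAP draws its rates from previous literature and an earlier telehealth trial. If its 50% already reflects incomplete uptake, a further allowance counts that twice. The 71% is therefore one end of a sensitivity range, not the trial's power.

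The objection does not remove the mismatch. The 104 and the 52 per group appear in Aim 2 and in the SAP's power basis, outside the Aim 1 context, and 116 randomized cannot be a randomized trial of 104.

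**Conclusion.** The sample sizes are incompatible, so at least one stated number is wrong. With 116 randomized, the SAP's own analysis rule gives 58 per arm, and the 52-per-group basis does not describe that analysis. With 104 randomized, the Aim 1 sentence is wrong.

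In power terms the choice between 58 and 52 per arm is modest: about 80% against about 77% at the planned rates. Non-uptake could matter more: at 58 per arm, about 71% to 76% if 6 TSM patients get none or half of the benefit. That range rests on three assumptions: the number 6, the benefit levels, and a 50% planning rate that refers to patients who use TSM.

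The documents do not show that a completer analysis is planned. The gap is that the fall from 58 to 52 has no stated reason, and its consequence for Aim 2 is not spelled out.

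**What to change.** 1. State one number randomized per arm in both documents: 58 (116 in total), or 52 (104 in total) if that was intended. The documents do not show which.
2. Reconcile it with Recruitment Procedures. Say how many patients were randomized before TSM enrolment ended, and whether patients assigned directly to standard of care count towards the control arm or the ITT set.
3. State that no randomized patient is replaced, or excluded from the primary Aim 2 analysis, for non-installation, non-use or withdrawal. Give the assumed loss with its reason, and say how missing outcomes are handled.
4. Keep 52 only as the number of TSM users expected for Aim 1 precision. The half-widths beside it need checking: 1.96 × √(p(1 − p)/52) gives 13.6%, 11.8% and 8.2% at 50%, 75% and 90%, where the protocol has 13.9%, 12.7% and 8.3%.
5. Restate power for the ITT number at 75% versus 50%: about 80% at 58 per arm or about 77% at 52. Add a labelled sensitivity range for non-uptake (71% to 76% at 58 per arm; 67% to 72% at 52). The SAP can keep 52 as the historical basis of its calculation, provided that it adds the power for the number analysed.
6. Rework the quality-of-life statement together with its group size. At 80% power and two-sided 0.05 (alpha assumed, not stated there), the detectable effect (1.960 + 0.842) × √(2/n) is 0.55 at 52 per group and 0.52 at 58, not 0.39.

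**Cost.** Wording in both documents, and possibly a less favourable stated power. If 116 was intended, no patients are added. If 104 was intended, choosing 116 would add 12, so the sponsor must first settle which number holds.

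### The three confidence-interval precisions quoted for satisfaction rates with 52 TSM patients do not come from one method; the clear error is 12.7% for a 75% rate

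*Protocol*

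**What the plan says.** The figures are in the protocol's statistical analysis section, under Aim 1. The sample size paragraph after Patient satisfaction sets the conditions, "For satisfaction rates of 50%, 75% and 90%, with a sample size of 52", and then states that "the corresponding 95% confidence intervals will have precision of +/- 13.9%, 12.7%, and 8.3" percent. The Upload compliance paragraph uses the first figure again: "With a sample size of 52 patients, the rates of compliance can be estimated to, at worst, +- 13.9%, with a 95% CI".

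The number 52 comes from the same sample size paragraph, where it refers to the TSM group: "We will randomize 116 patients as they are discharged from the hospital (58 per arm) in order to yield a maximum of 52 patients".

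No interval method is named for the Aim 1 rates. For the hospitalization and ER proportions in Aim 2 the protocol does name one: "Associated 95% confidence intervals for these proportions and their differences will be computed using exact methods". The SAP gives no precision statement for satisfaction or upload compliance that would replace these figures.

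**The concern.** The sample size, the three rates and the confidence level are all stated, so the half-widths should be reproducible once a method is chosen. They are not. The middle figure is also too close to the first: moving from a 50% rate to a 75% rate should narrow the interval by more than the protocol shows.

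Satisfaction and upload compliance are two of the five usability measures listed for Aim 1, and these are the only numerical precision statements given for them. As written, a reader cannot tell which kind of interval will be reported, or whether the quoted widths are too wide or too narrow for it. What is at stake is the accuracy of a descriptive statement. No test or decision rule uses it.

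**Working it through.** **Inputs.** From the Aim 1 text: n = 52; p = 0.50, 0.75, 0.90; 95% two-sided confidence; stated half-widths 13.9, 12.7 and 8.3 points.

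**Step 1: normal interval.** Half-width = 1.96 × √(p(1−p)/n).

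- p = 0.50: 1.96 × √(0.25/52) = 1.96 × 0.06934 = 13.59 points
- p = 0.75: 1.96 × √(0.1875/52) = 1.96 × 0.06005 = 11.77 points
- p = 0.90: 1.96 × √(0.09/52) = 1.96 × 0.04160 = 8.15 points

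The stated figures exceed these by about 0.3, 0.9 and 0.15 points.

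**Step 2: other methods at n = 52.** Half-widths in points. For the methods that are not symmetric away from 50%, the value is the average of the two sides.

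| Method | 50% | 75% | 90% |
|---|---|---|---|
| Stated in the protocol | 13.9 | 12.7 | 8.3 |
| Normal, 1.96 | 13.59 | 11.77 | 8.15 |
| Normal, multiplier 2 | 13.87 | 12.01 | 8.32 |
| t with 51 df | 13.92 | 12.06 | 8.35 |
| Normal, continuity-corrected | 14.55 | 12.73 | 9.12 |
| Wilson | 13.11 | 11.49 | 8.34 |
| Wilson, continuity-corrected | 14.01 | 12.38 | 9.22 |
| Agresti-Coull | 13.11 | 11.61 | 8.75 |
| Jeffreys | 13.28 | 11.55 | 8.15 |
| Exact (Clopper-Pearson) | 14.19 | 12.46 | 9.05 |

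No row gives the stated triple. A multiplier of 2 reproduces the first and third figures but gives 12.0 in the middle. The continuity-corrected normal interval reproduces the middle figure but gives 14.6 and 9.1 for the others.

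**Step 3: a check that does not depend on n or the multiplier.** For any interval of the form c × √(p(1−p)/n), the ratio of the half-width at 50% to that at 75% is √0.25/√0.1875 = 1.155. The stated ratio is 13.9/12.7 = 1.094. Rounding can raise it only to 13.95/12.65 = 1.103. So no choice of n or c in that formula reconciles the first two figures. The ratio of the first to the third is 13.9/8.3 = 1.675, against an expected 0.5/0.3 = 1.667, which agrees. The middle figure is therefore the one out of line.

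**Step 4: a possible source.** If the middle rate were 70%:

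- n = 50 with 1.96 gives 13.86, 12.70 and 8.32
- n = 52 with a multiplier of 2 gives 13.87, 12.71 and 8.32

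Either set rounds to all three stated figures. With 75% in place of 70%, both give 12.0.

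**Step 5: exact intervals, if they were chosen for Aim 1.**

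| Count | Rate | Below | Above | Average |
|---|---|---|---|---|
| 26/52 | 50% | 14.19 | 14.19 | 14.19 |
| 39/52 | 75% | 13.95 | 10.97 | 12.46 |
| 46/52 | 88.5% | 11.90 | 7.18 | 9.54 |
| 47/52 | 90.4% | 11.41 | 6.42 | 8.92 |

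Ninety percent of 52 is 46.8, which is not a possible count. Evaluating the limits at 46.8 gives an average of about 9.05, between the last two rows.

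**The case against.** The strongest reply is that little turns on this. Measured against the normal interval, every stated width is too wide, so precision is understated if anything, and the gaps are at most about 0.9 points. The precisions do not drive the sample size: the SAP justifies 52 per group by a chi-square comparison of hospitalization rates, and the Aim 1 text only describes what 52 patients would deliver. The intervals finally reported will come from the data. All of this stands, and it is why the point is minor. It does not make the 12.7% figure correct for a 75% rate.

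Three stronger readings are tempting, and the documents do not support them.

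- A reader might infer that all three figures are wrong. But 13.9% and 8.3% are obtained at n = 52 with the multiplier rounded to 2, and they are mildly conservative against 1.96.
- A reader might infer that the figures were assembled from different methods or different sample sizes. A single mislabelled rate explains all three equally well (Step 4). The documents settle neither explanation.
- A reader might infer that the compliance claim, "the rates of compliance can be estimated to, at worst, +- 13.9%, with a 95% CI", is false because the exact worst case is 14.2%. The exact method is named only for the Aim 2 proportions. Under the normal interval the worst case is 13.6%, so the claim is true and slightly cautious. It fails only if exact intervals are carried into Aim 1.

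**Conclusion.** The concern holds as a minor arithmetic inconsistency. At the stated n, rates and confidence level, no standard method tried yields 13.9%, 12.7% and 8.3% together. The clear error is 12.7% for a 75% rate, where the normal interval gives 11.8%: a gap of 12.7 − 11.77 = 0.93 points, or 0.93/11.77 = 8% in relative terms. The 13.9% and 8.3% figures are about 2% above their normal values.

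Whether the plan is cautious or optimistic depends on a method it has not named for Aim 1. Against normal intervals all the stated widths are conservative. Against exact intervals 13.9% (used twice) and 8.3% are slightly optimistic, and 12.7% is slightly conservative.

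The conclusion takes n = 52 as the plan states it. The protocol calls 52 a maximum, and fewer patients would widen every interval. The 70% explanation is an inference from the numbers only. Aim 2 power and the sample size are unaffected.

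**What to change.** In the Aim 1 text, name one interval method for the satisfaction and compliance rates, confirm whether the middle rate is meant to be 75%, and restate the four figures (three for satisfaction, one for compliance) at n = 52. For rates of 50%, 75% and 90%:

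- **Normal intervals:** 13.6%, 11.8% and 8.2%, with a compliance worst case of 13.6%.
- **Exact (Clopper-Pearson) intervals, if consistency with Aim 2 is wanted:** average half-widths of about 14.2%, 12.5% and 9.0%, with a compliance worst case of about 14.2%. For the 90% rate, say which count is used (9.5% at 46/52, 8.9% at 47/52). Give lower and upper limits instead of a single plus-or-minus figure, because these intervals are asymmetric away from 50%.

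If the middle rate was meant to be 70%, the normal value at n = 52 is 1.96 × √(0.21/52) = 12.5%.

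The cost is an edit to two sentences. Under the normal method all four figures become slightly narrower. Under the exact method three of the four (both uses of 13.9%, and the 8.3%) become slightly less favourable. Design, sample size and conduct do not change.

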Although many telehealth trials in community-dwelling seniors have been published, there is limited literature on the use of telehealth in *underserved populations*. The few telehealth studies conducted in disparity populations have focused primarily on diabetes and blood pressure management. Given the great discrepancy in prevalence rates of CVD disease and its manifestations between whites and ethnic minorities, coupled with the disparities in access to innovative and effective treatments between upper/middle and lower socioeconomic classes, it

is imperative that researchers and clinicians bring effective interventions to these at-risk populations.

The previous work of our research team includes a two-year randomized trial, a two-year matched control study, and a three-year randomized trial (currently underway). We have shown that TSM can create cost savings and shorter lengths of stay for those hospitalized. The present study proposes to test this technology with an underserved population to determine whether our previous results are generalizable.²⁶

OBJECTIVE(S)/SPECIFIC AIMS AND HYPOTHESES

Research Question: Can we narrow health disparities through TSM by providing the proposed disparity population with skills to monitor their health status daily and weekly access to a health practitioner through a scheduled telehealth video visit? We hypothesize that TSM patients will have significantly better outcomes: greater QoL and lower hospital utilization over 3 months than those receiving usual care.

In this study, we will apply appropriate and rigorous research methods to: *a*) assess patient acceptance and usability using a mixed methods approach; and *b*) directly compare TSM to standard of care in a health disparity population.

Aim 1: we will conduct a process evaluation to assess telehealth acceptance and usability among low-income, largely minority seniors living with CHF NYHA class 1-3.

We will use a mixed methods approach to look at indicators of usability, including qualitative measures, such as: 1) focus group feedback from key community stakeholders, including patients and caregivers, and quantitative measures, such as 1) rate of study participation acceptance; 2) self-monitoring behavior (as measured by vital sign uploads); 3) visit participation; 4) patient satisfaction; and 5) ease of use of measures.

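### The secondary length-of-stay comparison among hospitalized patients conditions on an outcome that TSM is expected to change, so it may be biased and should be reported descriptively

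*Protocol*

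**What the plan says.** The Protocol, under 2a (Measures of Inpatient Utilization), plans two analyses of LOS: "Cumulative LOS will be analyzed in two ways: intention to treat (ITT) analysis, and for only those hospitalized". The first is the main one: "The ITT analysis will include all patients, regardless of hospitalization history". The second is labelled secondary: "A secondary analysis will look at LOS only for those who experienced a hospitalization".

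The SAP keeps the same order of priority. It states "The primary analysis of this randomized clinical trial was based on intention to treat (ITT) principle, which included all subjects randomized", and for the LOS model "Cumulative LOS (inpatient days) was analyzed using a negative binomial regression". It then lists "Subgroup analyses included: patients hospitalized, heart class (2 vs. 3), and patients not receiving home care".

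Two other places bear on the point. Table 1 of the Protocol marks hospitalizations as a primary outcome variable. The SAP's sample-size paragraph says "We hypothesized that 75% of patients in the COM group would be hospitalized at least once during the study period", with 50% expected under TSM. Neither document calls the hospitalized-only comparison descriptive, or notes that randomization does not protect it.

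**The concern.** Heart class is fixed before treatment starts, so a comparison of arms within a heart class is still a randomized comparison. Being hospitalized during follow-up is different. It happens after randomization, and reducing it is what TSM is for. If TSM works as hoped, some patients who would have been admitted under control are not admitted under TSM. They then count in the control arm's hospitalized set but not in the TSM arm's. A difference in LOS between the two sets can come from this change in membership alone.

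What is at stake is interpretation. The Protocol's background reports from the team's previous work: "We have shown that TSM can create cost savings and shorter lengths of stay for those hospitalized". It goes on to say that the present study will find out whether the previous results generalize. A hospitalized-only difference in this trial could easily be read the same way, as an effect of TSM on how long patients stay.

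**Working it through.** **Inputs from the documents.** Hospitalized at least once: 75% control, 50% TSM. Patients per arm in the power calculation: 52. All are in the SAP's sample-size paragraph. Neither document gives a figure for LOS, so there is no stated LOS result to reproduce.

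**The one stated figure linked to the selection.** The SAP ties 52 per group to 75% versus 50%, by a two-sided 5% chi-square test, without stating the power. Recomputed with pooled variance, the power at 52 is 75.7%, and 80% would need 58 per group. This neither confirms nor refutes the 52, and the LOS point does not depend on it.

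**Size of the two sets.** Control: 52 × 0.75 = 39. TSM: 52 × 0.50 = 26. If TSM averts admissions and never causes one, 39 − 26 = 13 control patients, a third of the control set, have no counterpart in the TSM set.

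**Expected LOS ratio when no stay is changed.** Under that assumption 50% of patients are hospitalized under either arm, 25% only under control, and 25% under neither. Let m be the mean LOS of the first group and r·m that of the second; r is an assumption.

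- TSM, hospitalized only: m.
- Control, hospitalized only: (0.50·m + 0.25·r·m)/0.75 = m(2/3 + r/3).
- Ratio TSM/control, hospitalized only: 1/(2/3 + r/3).
- Ratio TSM/control, all patients: 0.50/(0.50 + 0.25·r).

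| r | Hospitalized only | All patients |
|---|---|---|
| 0.25 | 1.33 | 0.89 |
| 0.5 | 1.20 | 0.80 |
| 0.75 | 1.09 | 0.73 |
| 1 | 1.00 | 0.67 |
| 1.5 | 0.86 | 0.57 |
| 2 | 0.75 | 0.50 |

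The all-patient column is a real reduction in inpatient days, because admissions are averted. The hospitalized-only column reflects membership alone. At r = 0.5 the two point in opposite directions.

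**How often a nominal 5% test would reject.** This was simulated with 52 per arm, log-normal stays (log-SD 0.8, assumed), a t-test on log LOS and 6,000 runs. Rejection was 47% at r = 0.25, 17% at 0.5, 8% at 0.75, 5% at 1 and 10% at 1.5. With 75% hospitalized in both arms and r = 0.5, the ratio was 1.00 and rejection about 5%. These rates depend on the assumed distribution and test. They show the pattern and do not predict this trial's error rate.

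**Without the assumption that TSM never causes an admission.** In a model where one latent severity drives both admission and LOS, the ratio ran from 1.03 to 1.14. It was 1.00 when severity did not drive admission.

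**The case against.** The strongest reply is that the plan already has the right main analysis. LOS is analyzed in all patients, the restricted comparison is openly secondary, and the SAP's primary analysis is ITT. All of that stands. A reader who takes the plan to compare LOS only among the hospitalized would be mistaken.

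Second, bias is possible but not established. It needs both an effect of TSM on hospitalization and averted patients whose stays would have differed from the rest. If either is missing, the ratio is 1.00. That also stands. A reader might infer that the comparison must flatter TSM, but if the averted stays are the shorter ones, it makes TSM look worse.

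Third, shorter stays among the hospitalized are not this trial's stated hypothesis, which concerns quality of life and hospital utilization over three months. The background sentence describes previous studies. It makes a causal reading of the restricted result likely, but does not make that reading the claim under test.

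Fourth, the SAP's subgroup list names no outcome or test for hospitalized patients. Linking it to the Protocol's LOS analysis is the natural reading but is not spelled out.

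Covariate adjustment is a weaker defence. The Protocol's planned covariates are baseline measures, and they remove the selection only as far as they capture what determines both admission and length of stay.

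**Conclusion.** The point holds in limited form and is minor. The hospitalized-only LOS comparison conditions on a post-randomization primary outcome that the plan expects to move by 25 percentage points, so it may be biased as an estimate of TSM's effect on stay length. Under the SAP's rates, and if TSM only averts admissions and changes no stay, the ratio of means runs from 1.33 (r = 0.25) to 0.75 (r = 2). The documents give nothing from which to set r, so neither the size nor the direction can be known beforehand.

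Two stronger conclusions are not supported: that the comparison is certainly biased, and that the trial's LOS result as a whole is compromised. The all-patient ITT analysis does not select on hospitalization and is not affected.

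**What to change.** - Take hospitalized patients out of the SAP's list of subgroups, so that they do not stand beside heart class as if defined at baseline.
- Report LOS among the hospitalized by arm as description only (number of patients, median, range), with no p-value and no statement of treatment effect. Add a sentence that randomization does not protect the comparison. As the SAP is written in the past tense, the same labelling should apply wherever this result is reported.
- Draw any LOS conclusion only from the analysis of all randomized patients. As that is already the main analysis, this only rules out using the restricted result in its place. Either the SAP's negative binomial model or the joint test of the Protocol's Lachenbruch two-stage procedure will serve. The second stage should not be interpreted alone, because it uses only non-zero stays and so has the same selection.

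The cost is a few lines of SAP wording and one secondary p-value. No further patients or data are needed.
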